2.5 Analysis of the primary objective

The primary objective is to demonstrate the superiority of osilodrostat compared to placebo in achieving a complete response ($mUFC \leq ULN$) at week 12.

2.5.1 Primary endpoint

The primary efficacy variable is the proportion of randomized patients in each treatment arm who are complete responders at Week 12. A complete responder is defined as a patient who has $mUFC \leq ULN$ (based on central lab result) at Week 12. Patients who discontinued the study during the placebo-control period will be counted as non-responders for the primary endpoint. Dose reductions and temporary dose interruptions for safety reason during the placebo-control period do not preclude patients from being counted as a complete responder for the primary endpoint.

2.5.2 Statistical hypothesis, model, and method of analysis

For the primary objective, the statistical null hypothesis states that the complete response rates at the end of the 12-week placebo-controlled period (i.e., at Week 12) are the same between the two randomized arms. To test this hypothesis, a Cochran–Mantel–Haenszel (CMH) exact test stratified by the history of pituitary irradiation (yes/no) will be performed using the FAS. Following the ITT principle, patients are analyzed according to the drug and stratum they were assigned to at randomization.

If the 1-sided p-value is ≤ 0.025 , and the odds ratio (osilodrostat vs. Placebo) is > 1 , the null hypothesis will be rejected and the complete response rate in the osilodrostat arm will be considered higher than that in the placebo arm.

2.5.3 Handling of missing values/censoring/discontinuations

It is scheduled to collect three individual 24 hours Urine Free Cortisol (UFC) samples at visits Week 1, 12, 36, and 48, and two UFC samples at all other visits. For a given visit, Mean Urine

Free Cortisol (mUFC) is the mean of all available (with a minimum of 2) individual UFC values determined at a central laboratory. In the case that only one or no UFC value is available, the mUFC will be considered missing for that visit.

During the double blind period, early discontinued patients (prior to Week 12) will be followed at regular visits and have assessments performed as indicated in protocol visit evaluation schedule table (Table 7-1a). Patients who discontinued prior to Week 12 or had a missing mUFC assessment at Week 12 will be considered as non-responder in the primary analysis. No imputation will be used.

2.5.4 Supportive analyses

As a supportive analysis to the primary analysis, an un-stratified Fisher's exact test of the primary endpoint will be performed using FAS.

In addition, both stratified CMH exact test and un-stratified Fisher's exact test of the primary endpoint will be performed using PPS.

To deal with potential missing mUFC at Week 12, multiple imputation assuming missing at random will be performed as a sensitivity analysis. For patients who discontinued the study early, mUFC collected during the follow-up visit at Week 12 will also be used for sensitivity analysis. If mUFC during the follow up visit is missing at Week 12, the patient will be considered as a non-responder.

2.6 Analysis of the key secondary objective

The key secondary objective is to assess the complete response rate (proportion of enrolled patients with $mUFC \leq ULN$) in both arms combined at Week 36 in patients receiving osilodrostat treatment.

2.6.1 Key secondary endpoint

The key secondary efficacy variable is the proportion of complete responders at Week 36 in FAS patients receiving osilodrostat treatment. A complete responder is defined as an enrolled patient who has $mUFC \leq ULN$ at Week 36. Dose reductions and temporary dose interruptions for safety reasons do not preclude patients from being counted as a complete responder for the key secondary endpoint.

2.6.2 Statistical hypothesis, model, and method of analysis

For the key secondary endpoint, the statistical null hypothesis states that the proportion of complete response rate at Week 36 is $< 30\%$. The analysis of the key secondary objective will be based on the 2-sided 95% exact confidence interval (CI) constructed using the Clopper-Pearson method in FAS patients receiving osilodrostat treatment. Patients with missing mUFC at Week 36 will be counted as non-responders. If the lower bound of this 95% confidence interval is $\geq 30\%$, the null hypothesis will be rejected and the complete response rate will be considered at least 30% at Week 36. Patients randomized to placebo who do not switch to osilodrostat will not be included in this analysis.

The above testing on the key secondary objective will only be carried out if the null hypothesis for the primary objective is rejected. This sequential procedure will ensure preservation of the overall 2-sided type 1 error at 5%.

As supportive analysis of the key secondary objective, analysis will be repeated using PPS patients receiving osilodrostat treatment. In addition, the same analysis will be performed in the patients randomized to osilodrostat arm only. For each supportive analysis, the 2-sided 95% exact confidence interval of the complete response rate at Week 36 will be provided.

2.6.3 Handling of missing values/censoring/discontinuations

Placebo patients who discontinued during Period 1 and not received osilodrostat treatment in this study will not be included in the analysis. Patients who received osilodrostat treatment with missing mUFC at Week 36 will be considered as non-responders for key secondary analysis. In order to evaluate the impact of missing mUFC, multiple imputations assuming missing at random will be considered as sensitivity analyses.

2.7 Analysis of secondary efficacy objectives

2.7.1 Assess the overall response rate at Week 12, Week 36, and Week 48

Proportion of complete responders (enrolled patients with $mUFC \leq ULN$), partial responders (enrolled patients with $mUFC > ULN$ and at least 50% reduction from baseline), and overall responders (enrolled patients with $mUFC \leq ULN$ or have at least 50% reduction in mUFC from baseline and $> ULN$) will be summarized using point estimates for every scheduled visit in the core and extension phase at which UFC is collected by treatment arm. Response rate will also be provided for all patients in the open-label period. 95% 2-sided CIs will be provided at Week 12, Week 36 and Week 48. To calculate the response rate during the open label treatment period, for the osilodrostat arm, the denominator will be the number of patients randomized to osilodrostat in Period 1; whereas for the placebo arm, the denominator will be the number of patients randomized to placebo in Period 1 who switched to osilodrostat. The FAS will be used for this analysis.

2.7.2 Assess the change in mUFC during the Core and Extension periods of the study

- Change in mUFC from baseline during the placebo-control period only

2.7.3 For the actual value and change in mUFC from baseline during placebo-control period, descriptive summaries will be provided. Compare the time-to-first control of mUFC during the placebo-controlled period between patients randomized to osilodrostat and placebo

Time-to-first control of mUFC is defined as the time (in days) from first study treatment date to the time of the first post-baseline mUFC collection that was $\leq ULN$ (based on central lab result) before discontinuation or completion of placebo-controlled period, whichever is earlier. It will be defined as censored at the last mUFC collection date if the mUFC was not controlled during the placebo-controlled period.

Time-to-first control of mUFC during the placebo control period will be analyzed using Kaplan-Meier plots and the logrank test. The quantiles of time-to-first control and corresponding two-sided 95% CI will be calculated using Kaplan-Meier methodology. FAS will be used for this analysis.

2.7.4 Assess the time-to-escape during treatment of osilodrostat up to Week 48

Escape is defined as the first loss of control of UFC that meets all of the following criteria:

- prior normalization of UFC has occurred ($mUFC \leq ULN$)
- patient reached highest tolerated dose of osilodrostat
- 2 consecutive mUFC (collected at scheduled visits) were above 1.3x ULN
- the loss of control of UFC is not related to a dose interruption or dose reduction due to safety reasons
- happens beyond Week 26 when the patients have a chance to be treated with doses as high as 30 mg bid

Time-to-escape is defined as the time (in weeks) from the first collection of post-baseline normal mUFC ($\leq ULN$) to the first mUFC $> 1.3 \times ULN$ on 2 consecutive scheduled visits on the highest tolerated dose of osilodrostat and not related to a dose interruption or dose reduction due to safety reasons after Week 26.

The highest tolerated dose is defined as

- 30 mg bid if reached, or
- being on a reduced dose due to safety reasonse such as AEs, or
- being on the same dose for at least 3 scheduled visits if the previous two criteria are not met.

For patients who attained normal mUFC ($\leq ULN$), time-to-escape will be analyzed using Kaplan-Meier plots. This will be performed by randomized treatment assignment and for the overall trial population using FAS. The quartiles of time to escape and corresponding two-sided 95% confidence interval will be calculated using Kaplan-Meier methodology. In addition, time-to-escape will be summarized using descriptive statistics for patients who escape. Time-to-escape will not be assessed for patients during the first 26 weeks.

Patients that have dose interruption or dose reduction for safety reasons will be censored at the time of the first dose interruption. Patients who discontinued the study are considered as censored. Patients who were controlled until the end of the study will be censored at the last mUFC collection date. FAS will be used for this analysis.

2.7.5 Assess the change from baseline in cardiovascular and metabolic related parameters associated with Cushing's disease during the core period of the study

For cardiovascular and metabolic parameters associated with Cushing's disease (e.g. fasting glucose, HbA1c, fasting lipid profile, SBP, DBP, weight and waist circumference):

For actual value and change from baseline to Week 12, Week 36 and Week 48, descriptive summaries will be provided by treatment arm and for overall patients in open-label period.

For the actual value and change from the baseline to Week 12 or the last available measurement of the placebo control period, whichever occurs earlier, in addition to the descriptive summary, the mean difference between two randomized arms and associated 2-sided 95% C.I. will be estimated with adjustment for corresponding baseline parameter value. In addition, shift tables using normal/abnormal categories for BP (SBP, DBP), FPG, HbA1c, fasting lipid profile, weight and waist circumference from baseline to Week 12, 36, and 48 by randomized arms and for overall patients during the open-label period will be assessed. Normal for these parameters is shown in protocol Appendix 4. FAS will be used for this analysis.

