Escape	Defined as loss of control of mUFC after week 26 (mean UFC $>$ 1.3 x ULN on two consecutive visits on the highest tolerated dose of osilodrostat and not related to a dose interruption or dose reduction due to safety reasons) after prior mUFC normalization
Optional extension phase	Week 48 through Week 96
Study drug	Osilodrostat or placebo
Medication number	A unique identifier on the label of each blinded study drug package linked to one of the treatment groups of a study
mUFC	mUFC at a particular visit is the arithmetic mean of the urinary free cortisol (UFC) levels calculated from three 24-hour urine samples collected at screening, baseline, Week 12, Week 36, Week 48 and Week 12 follow up. The arithmetic mean of UFC from two 24-hour urine samples will be evaluated at all other study visits
Overall Response	Defined as either complete response (mUFC \leq ULN) or partial response (mUFC $>$ ULN with \geq 50% reduction from baseline) during study treatment
Partial Response	Defined as mUFC $>$ ULN with \geq 50% reduction from baseline during study treatment
Period	Period 1: Day 1 through Week 12. Period 2: Starts immediately after the Week 12 visit through Week 48.
Randomization number	A unique treatment identification code assigned to each randomized patient, corresponding to a specific treatment arm assignment
Subject Number (Subject No.)	A unique identifying number assigned to each patient/subject/healthy volunteer who enrolls in the study
Study drug discontinuation	Point/time when patient permanently stops taking study drug for any reason
Variable	Identifier used in the data analysis; derived directly or indirectly from data collected using specified assessments at specified time-points
Withdrawal of Consent	Withdrawal of consent occurs only when a patient does not want to participate in the study any longer, and does not want any further visits or assessments, and does not want any further study related contact

Amendment 2 (20-Dec-2019)

Amendment rationale

As of 10 December 2019, the study is fully enrolled and 45 patients are still on treatment. Of the 45 patients on treatment, 10 are active in the core phase of the study and 35 are active in the optional extension phase of the study. The last patient enrolled in the study should complete the 48 week core period by the end of Feb-2020.

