- Section 10.5.2.2 Assess the change in mUFC during the Core and Extension periods of the study: updated the section title to optional Extension periods
- Section 10.5.3.4 Other safety data: updated to clarify that tumor invasiveness is also evaluated
- Reference: FDA Guidance for Industry Suicidality corrected from 2015 to 2010 to match protocol referenced in Section 10.5.3.4 under the Columbia Suicide Severity Reporting Scale (C-SSRS)
- Reference: added Masri-Iraqi et al, 2014 to match reference in Section 2.6
- Clarifications were made in the protocol that extension phase is an optional extension phase

IRBs/IECs

A copy of this amended protocol will be sent to the Institutional Review Board (IRBs)/Independent Ethics Committee (IECs) and Health Authorities.

The changes described in this amended protocol require IRB/IEC approval prior to implementation.

The changes herein affect the Informed Consent. Sites are required to update and submit for approval a revised Informed Consent that takes into account the changes described in this protocol amendment.

Amendment 1 (20-Nov-2017)

Amendment rationale

As of 20 Nov 2017, 18 patients have been enrolled (treated) in the study.

The main purpose of this amendment is to align the language of all ongoing studies in Cushing's disease indication for prohibited drugs due to TdP risk and to add a statement regarding the risk of neutropenia observed in LCI699C2201 and LCI699C2103. These were newly acquired information added to the Investigator's Brochure for transparency, and are thus being added to all protocols. New objectives and endpoints on cortisol biomarkers were added to maintain consistency between the protocol and data collection occurring in the study, as described in the VES.

The duration of the optional extension period was increased in order to collect additional long-term safety and efficacy data as well as to provide continued access to the study drug for those patients benefitting from the treatment until a separate long-term safety study is set up at participating sites. Based on this extension, the end of study definition has been updated.

This protocol amendment introduces the following changes:

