PD	Protocol deviations
PPS	Per-Protocol Set
PRO	Patient-reported Outcomes
PT	Preferred term
qd	Qua'que di'e / once a day
QoL	Quality of Life
QTcF	QT corrected (Fridericia QT formula)
SAE	Serious adverse events
SAP	Statistical Analysis Plan
SBP	Systolic blood pressure
SOC	System Organ Class
SS	Safety Set
SSD	Study specific document
TBIL	Total bilirubin
TDM	Trial Design Model
TV	Trial Visit
UFC	Urine Free Cortisol
ULN	Upper Limit of Normal
WHO	World Health Organization

1 Introduction

This statistical analysis plan (SAP) describes the planned statistical analysis for the primary clinical study report (CSR) of study LCI699C2302. The analysis will be performed after all patients have completed 48 weeks treatment (the core phase of the study) or discontinued earlier. Data from extension phase will be included in the analysis if prior to data cut-off.

This SAP is formulated according to the information provided in the study protocol. All decisions regarding to the analysis described here, have been made prior to database lock and unblinding of study data.

[figure not shown]

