2.1 Data analysis general information

The primary analysis will be performed when all enrolled patients have completed the Core phase of study (Period 1 and 2) or have prematurely withdrawn from the study prior to the end of the Core phase at Week 48. The results and outcomes of this analysis will be presented in a CSR. After the Core study phase, patients receiving clinical benefit from osilodrostat treatment have the option to enter a 48-week extension phase. The additional data collected in the extension phase, will be further summarized in a final study report once these patients completed the study. There is no interim analysis planned for this study.

Novartis or designated CRO will analyze all data using the SAS System for data analysis V9.4 or higher. Any data analyses carried out independently by an investigator should be submitted to Novartis and approved before publication or presentation.

The data from all centers participating in the trial will be combined, so that an adequate number of patients will be available for analysis. The statistical analysis methods described in this section will focus on the analysis of the data in the Core study. Similar methods will be applied to the analyses in the extension phase as appropriate.

All data with an assessment date or event start date (e.g. vital sign assessment date or start date of an adverse event) prior to or on the cut-off date will be included in the analysis. Any data collected beyond the cut-off date will not be included in the analysis and will not be used for any derivations.

The randomization will be stratified by history of pituitary irradiation. To take stratification into account, the primary efficacy endpoint will be analyzed using Cochran-Mantel-Haenszel (CMH) exact test.

Categorical data or qualitative characteristics of a subject (e.g., gender, race, subject disposition, etc.) will be summarized by frequency count (number of subjects) and percentages. Percentages will be calculated using the number of subjects in the relevant population or subgroup as the denominator.

Continuous data (e.g., age, body weight, etc.) will be summarized by appropriate descriptive statistics (mean, standard deviation, median, minimum, and maximum).

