For calculation of proportion of responders beyond Week 48 (e.g. a time point in extension phase), the following rules will be applied to determine whether patients are included in the analysis.

- 1) patients who declined to enter optional extension phase after completion of the core phase will be excluded.
- 2) patients who completed the extension phase will be included until their individual end of study dates (EOT EXT visit, as per Protocol Amendment 02)
- 3) patients who discontinued prior to the data cutoff date for the Final DBL will be included for visits they could have completed if they had continued until week 96 or data cut off for the analysis (whatever occurs earlier), but excluded for further visits. For example, if the last completed scheduled visit for an early discontinued patient is Week 84, and the time between data cutoff and last completed scheduled visit is 20 weeks, he/she will be included in the analyses up to Week 96.

If included in the analysis for calculating the proportion of responders at a given timepoint, patients who discontinued before this timepoint will be counted as non-responders.

Criteria of adequate follow-up for time points in the extension phase

For a given time point in the extension phase, it will be considered to have adequate follow-up to be included in the reporting activities if there are at least 15 patients available for the analysis at that time point.

Time unit

A year length is defined as 365.25 days. A month length is 30.4375 days (365.25/12). If duration is reported in months, duration in days will be divided by 30.4375. If duration is reported in years, duration in days will be divided by 365.25.

Baseline

Baseline values for efficacy and safety evaluations are defined as the last assessment available before or on the start date of study treatment. If patients have no assessments as defined above, the baseline result will be missing.

Follow up

Regular safety follow-up is scheduled at 30 days after the last date of study treatment. In addition, for patients who discontinued study treatment during Period 1 (Weeks 1 to 12), reasonable efforts should be made to follow the patients and perform the assessments as indicated in protocol visit evaluation schedule table (protocol Table 7-1a) up to and including Week 12.

Visit number and time window

The following visit schedule tables are generated from TDM/TV domain.

Table 2-1 Scheduled visits in core phase

Core study Visit	Day/Week	Clarifying Notes

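### Core SAP 2.7.1 reports response at extension visits but gives only fixed denominators; on the natural reading, patients not yet due at Weeks 60 to 84 count as non-responders in the Week 48 report

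*SAP*

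**What the plan says.** The file holds two SAPs: the core SAP (01-Apr-2019) for the Week 48 report, and the final SAP (01-Dec-2020) for the report after the extension.

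- **Visits.** Core SAP 2.7.1 states that the three response proportions "will be summarized using point estimates for every scheduled visit in the core and extension phase at which UFC is collected by treatment arm". Core SAP 1.1.4 places the extension mUFC assessments that guide dosing at Weeks 60, 72 and 84.
- **Denominators.** Section 2.7.1 introduces these for the open-label treatment period: "for the osilodrostat arm, the denominator will be the number of patients randomized to osilodrostat in Period 1". For the placebo arm it uses those placebo patients who switched to osilodrostat. The analysis set is the FAS.
- **Timing.** Core SAP 1 and 2.1 run the analysis once all patients have completed Week 48 or left earlier. Section 1 adds: "Data from extension phase will be included in the analysis if prior to data cut-off". Section 2.1 bars anything after the cut-off from any derivation.
- **Missing mUFC.** Core SAP 2.5.3, 2.6.2 and 2.6.3 state a non-responder rule for Week 12 and Week 36 only.
- **Later text.** Final SAP 2.1.1 keeps all randomized patients in the denominator only up to Week 48. After that it excludes patients who declined the extension, and "patients who discontinued prior to the data cutoff date for the Final DBL will be included for visits they could have completed" by Week 96 or the cut-off. It reports an extension time point only if at least 15 patients are available. The core SAP has none of these rules.

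**The concern.** When the last patient reaches Week 48, patients enrolled in the preceding months are in the extension but have not reached its later visits. They have no mUFC there and cannot enter the numerator. If they stay in a fixed denominator, each one lowers the printed rate exactly as a treatment failure would. No separate missing-data rule is needed for that to happen. The share of such patients grows from Week 60 to Week 84, so the printed rate declines even if control of mUFC is perfectly maintained. Patients who finished the core and chose not to enter the extension have the same effect. The Week 48 report carries the primary result, and this table sits beside it.

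**Working it through.** The plan states no figure for extension response, so there is none to reproduce. The 60% below is its planning rate for Week 36 (core SAP 3), used purely as an illustration.

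**Inputs**
- Planned N = 69, i.e. 46 + 23 (core SAP 1.1). The achieved N is not in the documents. Using 69 as a fixed denominator also assumes that every placebo patient switched.
- Protocol, Amendment 1 rationale: "As of 20 Nov 2017, 18 patients have been enrolled (treated) in the study".
- Protocol, Amendment 2 rationale: "The last patient enrolled in the study should complete the 48 week core period by the end of Feb-2020". The same paragraph gives 10 patients still in the core phase on 10-Dec-2019.
- Assumed: cut-off 29-Feb-2020, constant true response of 60%, and no discontinuations or extension decliners. Under a fixed denominator either of the last two would lower the rate further.

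**Formula.** Printed rate = true rate × (N − patients who cannot have reached the visit) / N.

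**Check 1: the documented count at Week 60.** From 10-Dec-2019 to 29-Feb-2020 is 81 days, or 11.6 weeks. A patient still short of Week 48 on the first date is at most at about Week 59.6 on the second, so essentially none of the 10 can have a Week 60 mUFC. Unreachable share = 10/69 = 14.5%. Printed rate = 0.60 × 59/69 = 51.3%.

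**Check 2: accrual model for all three visits.** The last Day 1 is 48 weeks before the cut-off, about 30-Mar-2019. The remaining 69 − 18 = 51 patients therefore enter over W = 70.7 weeks from 20-Nov-2017. A visit at Week v is unreachable for anyone entering in the last k = v − 48 weeks of accrual.
- Uniform accrual: 51 × k/W.
- Back-loaded (rate rising linearly from zero): 51 × [1 − ((W − k)/W)²].
- Front-loaded (rate falling linearly to zero): 51 × (k/W)².

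| Visit | k | Unreachable, uniform | Printed, uniform | Unreachable, front to back | Printed, front to back |
|---|---|---|---|---|---|
| Week 60 | 12 | 8.7 (12.5%) | 52% | 1.5 to 15.8 | 59% to 46% |
| Week 72 | 24 | 17.3 (25%) | 45% | 5.9 to 28.7 | 55% to 35% |
| Week 84 | 36 | 26.0 (38%) | 37% | 13.2 to 38.7 | 49% to 26% |

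The uniform figure of 8.7 at Week 60 agrees with the 10 patients documented. The front-loaded figure of 1.5 does not, so that end of the range is unlikely at Week 60. With N = 73 instead of 69, the uniform results move by less than one percentage point. With a denominator limited to patients who could have reached the visit, a true 60% prints as 60% throughout.

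**Does the denominator sentence cover the extension?** Three places say yes. Core SAP 1.1.4 calls the extension open-label. Core SAP 4 divides efficacy reporting into only two periods, placebo-control and open-label. The mUFC-change endpoint in core SAP 1.2 spans core and extension and then adds all-patient results for the open-label period. Against that, Table 2-1 attaches the label to Period 2 visits, and Table 2-2 labels later visits as extension.

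**The case against.** The strongest reply is that this is silence in the plan and not a biased rule. The denominator sentence can be confined to Period 2. Core SAP 2.1 takes percentages over the relevant population or subgroup, and says similar methods apply to the extension as appropriate, which leaves room for a denominator of patients due. Non-response for missing mUFC is stated only for Weeks 12 and 36.

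That stands as far as it goes: carry-over is the natural reading, not an express instruction. But on the narrower reading, the SAP commits to extension rates with no denominator at all, and the choice would be left to the time of analysis. Either reading needs a rule.

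A reader might also infer more than the documents support:
- **That the denominators are all randomized patients.** They are not; the placebo arm counts only those who switched.
- **That the main efficacy conclusions are affected.** Every patient can reach Weeks 12, 36 and 48 by the trigger. Section 2.7.1 gives confidence intervals only at those visits, and no hypothesis test uses extension data.
- **That the trial's long-term results are biased.** Core SAP 2.1 assigns the additional extension data to a final report, and final SAP 2.1.1 and 2.7.1 supply proper rules there.
- **That the plan would record loss of control where there was none.** Loss of control has its own analysis, time-to-escape by Kaplan-Meier with censoring (core SAP 2.7.4), which does not turn patients not yet due into failures.

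**Conclusion.** The point holds in limited form and is worth correcting. Read naturally, core SAP 2.7.1 produces descriptive extension response rates in the Week 48 report that decline because of the calendar; read narrowly, it leaves their denominator undefined.

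The best-anchored size is at Week 60, where a true 60% would print as about 51-52%. The Week 72 and Week 84 values (about 45% and 37%, with ranges of about 35-55% and 26-49%) depend on the shape of accrual. All of these are illustrations resting on the carry-over reading and the assumptions listed with the calculation, not forecasts of the reported table.

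**What to change.** In core SAP 2.7.1, for visits after Week 48, adopt the rules of final SAP 2.1.1, adapted to a cut-off at which patients are still on treatment:

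1. Exclude patients who completed the core phase and declined the extension. They must be named, because core SAP 2.3.2 does not count them as discontinuations and a rule on discontinuers alone would leave them in the denominator.
2. Include all other patients only at visits whose scheduled date (Day 1 plus visit day) is on or before the data cut-off.
3. Count discontinuers among them as non-responders.
4. Report a visit only if at least 15 patients are available.

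Alternatively, stop the core table at Week 48 and leave extension visits to the final report. If extension visits are kept, show the number due and the number assessed at each one.

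The cost is a few lines of SAP text and a date filter in the table program. The downside is fewer patients, and so less precise rates, at the late visits.
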